### 1.4. Efficacy Analysis

Listings, tables, and figures of efficacy variables will be based on the full analysis population.

#### 1.4.1. Primary Efficacy Analyses

The baseline, post-baseline and change from baseline for number of micturition episodes in 24 hours, number of incontinence episodes in 24 hours as well as volume voided will be summarized by treatment group using descriptive statistics and presented graphically at each scheduled time point. The differences between treatment effects within sequence can be assessed by means of a paired t-test for samples using the intra-individual differences between the outcomes in both periods as the raw data. Comparison of the active treatment to placebo will be tested at the one-sided significance level 0.10 by means of the corresponding contrast. Plots of the mean change from baseline, 90% confidence Intervals (CIs) will be produced by treatment group.

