**Number of Participants:**

It is estimated that up to 150 subjects will be screened to yield approximately 75 subjects that will enter Single-blind Run-in Period to yield approximately 44 subjects that will enter the Double-blind Treatment Period. A sample size of 38 completers will have 81% power to detect a treatment difference in means of numbers of micturition per 24 hours of 0.5, assuming a standard deviation of differences of 1.4, using a paired t-test with a 10% one-sided significance level. Assuming a 15% dropout rate, a sample size of 44 would be needed.

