## 1.2. Schedule of Assessments

**Table 1. Schedule of Assessments: Pre-randomization Phase**

Period	Screening/ washout	Single-blind Run-in	
Day	-42 to -16	-15	-1
Clinic Visit A	V1	V2 B	V3
Assessment			
Informed consent	X		
Medical history	X		
Demographics	X		
Inclusion/exclusion	X	X	X
Physical exam, full	X		
Physical exam, brief		X	X
Vital signs	X	X	X
Clinical labs (chem/heme/urine)	X	X	X
Urine culture test	X	X	X
Urine drug screen	X		X
Serum pregnancy test	X		
Urine pregnancy test		X	X
12-lead ECG	X	X	X
C-SSRS	X	X	X
Concomitant medications	X	X	X
Adverse events	X	X	X
BPIC-SS C , MESA-IQ C	X	X	X
PPBC		X	X
OAB-q LF		X	X
SGRA		X	X
ESS		X	X
SISQ (diary)		Once daily, in morning	
Void Diary assessment (includes PPIUS)		During the week prior to clinic visit (V3), subject will record micturition time, type, and urgency for each episode for a minimum of 3 and up to 7-days; and will also record urine volume during 2-day weekend (or other 2-day timeframe convenient to subject work/life schedule).	
Study drug dosing (diary)		Once daily, in evening	
Diary/dosing instruction		X	X
Dispensing study drug		X	X
Drug accountability			X
OAB Symptoms characterized		X D	
Randomization criteria checklist			X
Randomization			X

ABPIC-SS= Bladder Pain/Interstitial Cystitis Symptom Score; CSSRS= Columbia-Suicide Severity Rating Scale; ECG= Electrocardiogram; ESS= Epworth Sleepiness Scale; MESA-IQ= Medical, Epidemiologic and Social Aspects of Aging incontinence questionnaire, OAB-q LF= Overactive Bladder Questionnaire long form; PPBC= Patient Perception of Bladder Condition; PPIUS= Patient Perception of Intensity of Urgency Scale; SGRA= Subject Global Response Assessment; SISQ= Symptom Impact on Sleep Questionnaire; V= Visit.

BVisit window is  $\pm 1$  day. BVisit 2, Day -15, is end of Screening/Washout Period and start of the Single-blind Run-in Period. At visit 2, a subject that has met all inclusion/exclusion criteria, has stopped their current medication treatment for OAB, and has completed all study procedures, will be dispensed single-blind study-drug with instruction to ingest first dose that evening 30 minutes before bedtime. CExclusion criteria. DSee Section 8.1.2.8; this must be completed at the clinic visit on the same day that study drug is dispensed to subject; the subject will ingest first dose of study drug that evening.

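### Does listing three variables under Primary Efficacy Analyses, with the one-sided 0.10 test tied to none of them, inflate the trial's error?

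*Combined protocol and SAP*

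**What the plan says.** Section 1.4.1 has three relevant sentences.

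- The first is descriptive: "number of micturition episodes in 24 hours, number of incontinence episodes in 24 hours as well as volume voided will be summarized" by treatment group and plotted at the scheduled time points.
- The second gives the method. The treatment difference "can be assessed by means of a paired t-test for samples using the intra-individual differences between the outcomes in both periods". It refers to outcomes in general and names none.
- The third sets the level: "Comparison of the active treatment to placebo will be tested at the one-sided significance level 0.10 by means of the corresponding contrast". It too names no variable.

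The section gives no test order, hierarchy or multiplicity adjustment.

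The synopsis item Number of Participants is specific. It powers the trial for a "treatment difference in means of numbers of micturition per 24 hours of 0.5", "using a paired t-test with a 10% one-sided significance level", assuming a standard deviation of differences of 1.4 and 38 completers. Incontinence episodes and volume voided have no target difference and no power calculation in the text reviewed.

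**The concern.** A heading that says primary, three variables beneath it, and a test sentence that picks none of them is a familiar route to a loose success criterion. If each variable were tested at one-sided 0.10 and any one could be reported as the positive primary result, the 10% used for the sample size would no longer describe the trial's chance of a false positive. Two variables with no planning behind them could also carry the trial when micturitions did not. With a level already as generous as one-sided 10%, a reader would want to know which result decides.

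**Working it through.** **Inputs.** From Number of Participants: 38 completers, difference 0.5, SD of differences 1.4, paired t-test, one-sided 0.10, stated power 81%. From section 1.4.1: three variables and one level, 0.10. The documents give no correlations between the variables, so those below are assumptions.

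**Step 1: reproduce the plan's figure.** The noncentrality is (0.5/1.4) × √38 = 0.357 × 6.164 = 2.20. With 37 degrees of freedom and one-sided 0.10, the noncentral t gives power of 81.5%. The normal approximation, Φ(2.20 − 1.28), gives 82.1%. A two-sided 0.10 test would give 69.7%. The stated 81% is therefore the power of a single one-sided 0.10 test on micturitions, with nothing set aside for a second or third variable.

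**Step 2: the error under the possible decision rules**, with one test per variable at one-sided 0.10:

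| Rule | False-positive probability |
|---|---|
| Micturitions alone decides | 10% |
| Fixed order, micturitions first | 10% |
| All three must be significant | at most 10% |
| Either of two, independent | 1 − 0.9² = 19% |
| Any of three, independent | 1 − 0.9³ = 27.1% |
| Any of three, correlation 0.3 | 24.2% |
| Any of three, correlation 0.5 | 21.8% |
| Any of three, correlation 0.7 | 19.0% |
| Any of three, correlation 0.9 | 15.0% |
| Any of three, upper bound | 3 × 0.10 = 30% |

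The correlated rows use an equicorrelated trivariate normal. Simulating three paired t-tests with n = 38 gives 24.3%, 21.9%, 19.0% and 15.2% for the same four correlations. Subtracting 10% leaves the part that comes only from the two other variables: 14.2%, 11.8%, 9.0% and 5.0%.

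**Step 3: which rule does the plan contain?**

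- The sentence listing the three variables provides for summaries and graphs, not tests.
- The test sentence speaks of one comparison and one contrast.
- The only place that joins this test and this level to a variable is Number of Participants, and the variable is micturitions.
- No sentence says that any one of the three suffices.

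The rules that the text supports are therefore in the 10% rows. The rows from 15% to 30% describe a rule that would have to be added.

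**Step 4: would formal adjustment help?** An equal split, 0.10/3 per variable, would cut power for micturitions to 62.5% with 38 completers. Restoring 80% would need 58 completers, and 58/0.85 = 68.2, so 69 subjects after 15% dropout. That is a heavy price to guard against a rule that the plan does not state.

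**The case for a change.** The strongest opposing argument is that a sample-size assumption is not an endpoint declaration. If the first sentence of section 1.4.1 is purely descriptive, the test has no named variable. If the outcomes in the second sentence refer back to it, there are three. Either way the section does not say which result decides, and one added sentence would settle it without touching the sample size or power.

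That description of section 1.4.1 is accurate and it stands. It does not show that the error is inflated or that different analysts would reach different primary results. The sample-size paragraph uses the identical test and level, and it leaves little doubt about the variable.

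Two further limits weaken the concern. First, section 1.4.2 and the fuller statistical analysis plan that section 1.3 mentions were not in the text reviewed, and either may name the primary variable, so its absence from the plan cannot be claimed. Second, this is a Phase 1b crossover of about 44 subjects, and the text reviewed sets no family-wise error goal.

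The inflation figures are also soft. Table 1 of section 1.2 shows one void diary in which the "subject will record micturition time, type, and urgency for each episode" and "will also record urine volume during 2-day weekend". This makes correlation plausible, but it gives no size, and it covers only the pre-randomization phase. The 30% ceiling assumes one test per variable at one time point.

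**Conclusion.** No change follows. Section 1.4.1 leaves a detail unwritten, and an analyst would fill it correctly from the sample-size statement: the one-sided 0.10 paired comparison decides on micturitions per 24 hours, and incontinence episodes and volume voided are supportive. On that reading the excess error is zero, and the planned 44 subjects and roughly 81% power stand as written.

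The excess of about 5 to 17 percentage points (15.0% to 27.1%, less 10%) arises only if all three variables are tested at 0.10 and any one is accepted as success, which the text reviewed does not provide for. The conclusion rests on reading section 1.4.1 together with Number of Participants, and on no unseen section setting an any-of-several rule. If the results were presented with incontinence episodes or volume voided as the deciding primary finding, the concern would apply to that report.

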#### 1.4.3. Safety Analyses

All safety data (adverse events [AEs], clinical laboratory results, vital signs, physical examinations, electrocardiograms [ECGs], and Columbia-Suicide Severity Rating Scale [C-SSRS] and Epworth Sleepiness Scale [ESS]) will be listed for subjects in the enrolled and randomized safety populations.

AEs will be categorized into Preferred Term (PT) and associated System Organ Class (SOC) using the Medical Dictionary for Regulatory Activities (MedDRA). Treatment-emergent adverse events (TEAEs) will be defined as AEs that start after or increase in intensity after the first dose of study drug. TEAEs will be summarized by presenting the incidence of AEs for each treatment group by the MedDRA PT, nested within SOC for the safety population. Medical history will be coded to MedDRA terms. Coded medical history terms will be summarized for all subjects in the randomized safety population.

Laboratory evaluations and vital signs will be summarized by treatment and time point for the randomized safety population. Concomitant and prior medications will be coded using the latest version of the World Health Organization Drug Dictionary (WHO-DD) and presented in tables and listings.

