**Brief Summary:**

The purpose of this study is to investigate the effects of oral administration of 1 mg/day V117957 each evening in female subjects with overactive bladder syndrome as compared to placebo. The study will consist of a Screening/ Washout Period (up to 4 weeks), Single-blind Placebo Run-in Period (2 weeks), Double-blind Treatment Period (8 weeks), Single-blind Placebo Washout Period (1 week), and Follow-up Period (up to 1 week).

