**Treatment Groups and Duration:**

V117957 (6-weeks) and Placebo (5-weeks).

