**Schema:**

Phase	Pre-randomization		Post-randomization										Single-blind washout	Follow-up
	Screening / washout	Single-blind Run-in	Double-blind Treatment											
Day	-42 to -16	-15	-1 A	1	14	15	28	35	42	49	56	63	70	
Clinic Visit	V1	V2	V3 A		V4		V5		V6		V7	V8	V9	
Phone call B				P1		P2		P3		P4				
Tx Sequence A		Placebo		Placebo	V117957								Placebo	
Tx Sequence B		Placebo		V117957						Placebo	Placebo			

A Visit 3, Day -1, is end of Single-blind Run-in Period and start of the Double-blind Treatment Period. At visit 3, a subject that has met all inclusion/exclusion criteria, has met all randomization eligibility criteria, and has completed all study procedures, will be dispensed double-blind study-drug with instruction to ingest first dose that evening 30 minutes before bedtime.

B Phone contact between clinic visits to assess tolerability and review diary/dosing instructions.

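### TEAE incidence is shown per treatment although scheduled time at risk is longer on V117957 under every reading, and the placebo weeks that count are not stated

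*Combined protocol and SAP*

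**What the plan says.** Section 1.4.3 (Safety Analyses) sets the summary measure: "TEAEs will be summarized by presenting the incidence of AEs for each treatment group by the MedDRA PT". It defines treatment-emergent events as "AEs that start after or increase in intensity after the first dose of study drug". It gives no end to that window, no rule for assigning an event to one of the two treatments that each subject takes, and no exposure-adjusted measure.

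The synopsis gives the durations as "V117957 (6-weeks) and Placebo (5-weeks" and the periods as "Single-blind Placebo Run-in Period (2 weeks), Double-blind Treatment Period (8 weeks), Single-blind Placebo Washout Period (1 week". In the Schema, Sequence A takes placebo and then V117957 within the double-blind period, and Sequence B takes them in the reverse order. Both take placebo in the run-in and in the washout.

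Which dose starts the window is open to two readings. Section 1.2 (Table 1, footnote B) calls the run-in placebo study drug and gives it a first dose at Visit 2. Schema footnote A says that a randomized subject "will be dispensed double-blind study-drug with instruction to ingest first dose that evening 30 minutes before bedtime" at Visit 3. Section 1.3 limits the safety population to randomized subjects who were dosed and had a safety assessment, but does not say which placebo weeks are counted.

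**The concern.** Crude incidence grows with the length of observation. If one column covers 6 weeks and the other fewer, the longer column tends to show more subjects with events even when the drug adds no risk. Here V117957 has the longer time under every way of counting placebo, and a reader of the table would not know how much longer.

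The count that comes nearest to equal time, 5 placebo weeks, gets there by pooling unlike weeks. Two are single-blind and come before randomization. One is the single-blind washout, which in Sequence A directly follows V117957, so a late drug event may be charged to placebo. In Sequence B the same can happen in the double-blind placebo weeks.

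What is at stake is how the side-by-side tolerability display is read. No safety test is planned.

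**Working it through.** **1. Reproduce the stated durations.** From the period lengths in the Brief Summary and the layout in the Schema:

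- Double-blind placebo = 8 − 6 = 2 weeks in each sequence.
- All placebo = 2 (run-in) + 2 (double-blind) + 1 (washout) = 5 weeks, as the synopsis states.
- V117957 in Sequence A: Days 15 to 56 = 42 days = 6 weeks. In Sequence B: Days 1 to 42 = 42 days = 6 weeks.

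**2. Exposure under each reading.** Subject-weeks = subjects × weeks, with no dropout. V117957 has 44 × 6 = 264, or 38 × 6 = 228 for the planned completers ("A sample size of 38 completers").

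| Placebo weeks counted | Weeks | Time ratio, V117957 to placebo | Placebo subject-weeks, N=44 | N=38 |
|---|---|---|---|---|
| Double-blind only | 2 | 3.0 | 88 | 76 |
| Double-blind + washout | 3 | 2.0 | 132 | 114 |
| Run-in + double-blind | 4 | 1.5 | 176 | 152 |
| All | 5 | 1.2 | 220 | 190 |

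**3. Which reading the text favors.** The synopsis states 5 placebo weeks, Table 1 calls the run-in placebo study drug, and Section 1.4.3 anchors events to the first dose of study drug. Together these favor 5 weeks but do not settle it.

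**4. Size of the spurious gap.** The documents give no event rate, so this step rests on assumptions: the same true risk on both treatments, a constant hazard, everyone completing, and p = two-week incidence. Incidence over w weeks = 1 − (1 − p)^(w/2).

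At p = 10%, V117957 = 1 − 0.9^3 = 27.1%. Placebo is:

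- 2 weeks: 10.0%, gap 17.1 points
- 3 weeks: 1 − 0.9^1.5 = 14.6%, gap 12.5
- 4 weeks: 1 − 0.9^2 = 19.0%, gap 8.1
- 5 weeks: 1 − 0.9^2.5 = 23.2%, gap 3.9

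The same formula over a range of p gives these gaps in points:

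| p | 6 vs 2 weeks | 6 vs 3 | 6 vs 4 | 6 vs 5 |
|---|---|---|---|---|
| 5% | 9.3 | 6.9 | 4.5 | 2.2 |
| 10% | 17.1 | 12.5 | 8.1 | 3.9 |
| 20% | 28.8 | 20.4 | 12.8 | 6.0 |

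These values of p suit a row for any event. For a single preferred term at p = 1% to 2%, V117957 = 1 − 0.99^3 = 3.0% to 1 − 0.98^3 = 5.9%. The gap is then 2.0 to 3.9 points against 2 placebo weeks, and 0.5 to 1.0 points against 5.

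**5. Sensitivity to the constant hazard.** If the hazard in weeks 3 to 6 of V117957 is k times that in weeks 1 to 2, the 6 vs 2 gap at p = 10% is 1 − 0.9^(1+2k) − 0.10. That is 9.0 points at k = 0.5, 4.6 at k = 0.25 and 0 at k = 0. Early onset therefore shrinks the gap.

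**6. Precision of an equal-length comparison.** Days 1-14, Sequence B (V117957) against Sequence A (placebo), assuming 22 per sequence: the 95% half-width is 1.96 × √(2p(1 − p)/22) = 12.9, 17.7 and 23.6 points at p = 5%, 10% and 20%.

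**The case against.** - **The silence may lie in the excerpt.** The available text is at summary level: its numbering passes from 1.4.1 to 1.4.3, and Table 1 points to a Section 8.1.2.8 that is not included. A reader might infer that the plan has no assignment rule and no exposure summary anywhere. The documents do not support that. What stands is that the stated measure is crude incidence and the scheduled times are unequal.
- **The best-supported reading is the mildest.** This is right. A reader might infer a threefold imbalance; that applies only if double-blind placebo alone is counted. With 5 weeks the gap is 2.2 to 6.0 points at p = 5% to 20%, about 1 to 3 of 44 subjects, and at most about 1 point for a rare preferred term.
- **The run-in could push the other way.** A reader might infer that clustering of events in the run-in makes V117957 look better, or that subjects with run-in events are selected out. The synopsis plans for "approximately 75 subjects that will enter Single-blind Run-in Period to yield approximately 44 subjects that will enter the Double-blind Treatment Period", so 75 − 44 = 31 run-in subjects fall outside the safety population. But the stated condition is that a subject "has met all randomization eligibility criteria"; nothing says that adverse events drive the attrition, and no onset pattern is given. These are possibilities, not findings.
- **Events may be sought less in the run-in.** The documents do not show this. Table 1 marks adverse events at Visits 1, 2 and 3, and the body of Table 2 is missing.
- **The remedy is noisier than the problem.** At p = 10% the Days 1-14 half-width (17.7 points) exceeds even the 6 vs 2 gap (17.1). This stands, and it is why that display can only supplement the main table.
- **The table is descriptive and the durations are stated.** This also stands, and it limits the harm to the display.

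**Conclusion.** The concern holds in a limited form. As written, the plan compares crude incidence over 6 weeks of V117957 with incidence over 2, 3, 4 or 5 weeks of placebo. Time is longer on V117957 in each case, and the text leaves the choice open while leaning to 5.

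Under equal risk, constant hazard, full completion and 10% two-week incidence, the table would show V117957 worse by 3.9 points on the favored reading and by 17.1 points on the double-blind-only reading. The durations and ratios follow from the documents; the sizes in points do not, because every rate is assumed. If hazards are not constant, the size changes and on the 5-week reading the direction is not fixed.

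No wrong test results. The point should be dealt with before unblinding because the design already supplies a randomized, equal-length contrast that the pooled table leaves unused.

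**What to change.** 1. Keep the incidence table. State which placebo weeks its placebo column counts, which is the sponsor's choice, and print subject-weeks of exposure for each column.
2. Whichever weeks are chosen, show run-in and washout placebo events separately from double-blind placebo events.
3. Add one display for Days 1-14 by randomized sequence: Sequence B on V117957 against Sequence A on placebo. Count events that start or worsen from the first double-blind dose (evening of Visit 3) to the Sequence A switch (Day 14/15). It is randomized, concurrent and equal in length, comes before any crossover carryover, and works under either starting dose for the event window.

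If a fuller section already sets the counting rule or an exposure table, a cross-reference to it meets that part of the request.

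Two further displays are optional. One sets the first 2 weeks of V117957 against the 2 double-blind placebo weeks within subject; it is not balanced for time on study. The other is exposure-adjusted rates, which need a warning that they assume a roughly constant hazard. With equal risk, p = 10% and all first events in the first 2 weeks, the rates are 4.4/264 = 0.017 against 4.4/88 = 0.050 per subject-week, a ratio of one third where the truth is 1. Censoring at first event barely helps (0.345).

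The cost is SAP wording and a few descriptive tables, with no new data. The Days 1-14 display has low precision (about 18 points either way at 10%) and cannot show later-onset events, so it does not replace the full table.

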**Overall Design:**

Phase 1b, multicenter, randomized, double-blind, placebo-controlled, crossover study

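### Section 1.4.3 has no rule for adverse events that start in placebo weeks after V117957; on the natural reading they count as placebo events and could narrow the safety contrast

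*Combined protocol and SAP*

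**What the plan says.** The study is a "Phase 1b, multicenter, randomized, double-blind, placebo-controlled, crossover study". The Brief Summary gives the periods as "Single-blind Placebo Run-in Period (2 weeks), Double-blind Treatment Period (8 weeks), Single-blind Placebo Washout Period (1 week), and Follow-up Period (up to 1 week"), and Treatment Groups and Duration gives the exposure as "V117957 (6-weeks) and Placebo (5-weeks").

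The Schema shows the order. Sequence A takes placebo, then V117957, then the single-blind placebo washout. Sequence B takes V117957, then double-blind placebo, then the same washout. No off-treatment gap is shown at either change from V117957 to placebo.

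Section 1.4.3 counts as treatment-emergent those "AEs that start after or increase in intensity after the first dose of study drug", and states that "TEAEs will be summarized by presenting the incidence of AEs for each treatment group by the MedDRA PT". Laboratory results and vital signs are to be summarized by time point as well as by treatment; adverse events by treatment group only.

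The text does not say what a treatment group is when each subject takes both treatments. It sets no window after the switch, no new reference for worsening when the treatment changes, and no separate place for run-in or washout events. The run-in placebo is itself called study drug in the notes to Table 1: at Visit 2 it "will be dispensed single-blind study-drug with instruction to ingest first dose that evening 30 minutes before bedtime". Read literally, the treatment-emergent window therefore opens in the run-in.

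**The concern.** Placebo in this design covers two states: placebo before any V117957, and placebo taken immediately after 6 weeks of it. One placebo column mixes them. If lingering exposure or the stopping of V117957 causes an event, that event starts while the subject is taking placebo. Counted there, it raises the comparator rate and lowers the difference between V117957 and placebo. It also does not show in the summary as an event of the weeks after the drug.

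This is separate from the unequal time on each treatment. It would remain if the periods were equally long or if rates replaced crude incidence. The missing rule is a problem in itself, because the same event could be credited to either treatment after the data have been seen.

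**Working it through.** **Inputs.**
- Run-in 2 weeks, double-blind 8 weeks, washout 1 week (Brief Summary).
- V117957 6 weeks and placebo 5 weeks per subject (Treatment Groups and Duration).
- About 44 subjects entering double-blind treatment (Number of Participants).
- Order of treatments from the Schema. Its layout is broken in the text I have, so the switch points are inferred from the order and the durations.
- Assumptions: 1:1 allocation (no ratio is stated in the sections I have), hence 22 per sequence, and full follow-up.

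**Step 1: reproduce the plan's 5 placebo weeks.** Double-blind placebo is 8 − 6 = 2 weeks. Run-in 2 + double-blind 2 + washout 1 = 5, as stated. Without the weeks after V117957 the count would be 2 + 2 = 4 in Sequence A and 2 in Sequence B. The stated 5 therefore includes post-V117957 weeks in both sequences, under a heading that names the two treatments, not the sequences, as the groups.

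**Step 2: share of placebo time that follows V117957.**

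| Placebo time | Person-weeks | After V117957 |
|---|---|---|
| Run-in | 44 × 2 = 88 | 0 |
| Double-blind, Sequence A | 22 × 2 = 44 | 0 |
| Double-blind, Sequence B | 22 × 2 = 44 | 44 |
| Washout | 44 × 1 = 44 | 44 |

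- Double-blind placebo only: 44/88 = 50%, all of it in Sequence B.
- With the washout week: 88/132 = 67%.
- With the run-in as well: 88/220 = 40%.

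**Step 3: what that share could do.** Let r0 be the event rate on placebo before V117957, r1 the rate on V117957, s the share from step 2, and c the fraction of the excess r1 − r0 that persists in post-V117957 placebo weeks. The value of c is unknown; I hold it constant over those weeks for simplicity. The pooled placebo rate is r0 + s × c × (r1 − r0), so the observed rate difference is (1 − s × c) times the true one.

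| s | c = 0 | c = 0.25 | c = 0.5 | c = 1 |
|---|---|---|---|---|
| 50% | 100% | 87.5% | 75% | 50% |
| 67% | 100% | 83.3% | 66.7% | 33.3% |
| 40% | 100% | 90% | 80% | 60% |

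The cells give the percentage of the true rate difference that remains. With c = 0 nothing is lost. A discontinuation effect could exceed c = 1. The documents supply no value for c, r0 or r1, so the table shows a range and does not estimate a bias.

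**Step 4: the exposure effect, which runs the other way.** Section 1.4.3 plans crude incidence over 6 weeks of V117957 against 2 weeks of double-blind placebo. If V117957 had no effect and 10% of subjects (assumed) had an event in 2 weeks at constant hazard, incidence over 6 weeks would be 1 − 0.9³ = 27%. Unequal exposure alone would then show a gap of about 17 points against V117957. Crude incidence thus carries two distortions of opposite sign, and the documents do not allow their net to be worked out.

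**The case against.** The strongest reply is that the plan never says these events go to placebo. It speaks only of treatment groups, and assignment by treatment at onset, by last active treatment or by sequence would each fit the words. That stands as far as it goes: no attribution rule is written. The 5-week placebo total does point to treatment at onset, however, and if several readings are possible the rule still has to be fixed in advance.

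A reader might go further and infer that the comparator is contaminated and a V117957 signal hidden. The documents do not support this. The text available gives no half-life and no evidence of a residual or discontinuation effect, and without one this mechanism adds no bias. Onsets during V117957 still count for V117957, the double-blind placebo weeks of Sequence A are free of earlier drug, and longer exposure to V117957 pushes crude incidence in the opposite direction.

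A reader might also infer that the washout week was placed to observe discontinuation events. The Brief Summary only names the period; it gives no such purpose.

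It is also fair to say that the safety summaries involve no hypothesis test and that all safety data are listed by subject, so events could be reassigned later. A reassignment chosen after unblinding is not a substitute for a prespecified table. Finally, the sections I have stop at 1.4.3, and a rule elsewhere in the full protocol or SAP cannot be excluded. If there is one, Section 1.4.3 should point to it.

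**Conclusion.** The point holds as a gap in the planned tabulation. Placebo follows V117957 directly, and the summary has one placebo group with no rule for onsets after the switch. On the natural reading, any event that V117957 causes after it is stopped would be counted against placebo, which would narrow the contrast.

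The shares of placebo time at issue are 50%, 67% or 40%, depending on whether the washout and run-in are counted. They rest on 1:1 allocation, full follow-up and the switch points inferred from the Schema. The size of any bias cannot be derived from the documents and may be zero.

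The case for change is that a better table is available at little cost. It does not depend on bias having been shown. The efficacy analysis and sample size are not affected.

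**What to change.** In Section 1.4.3, before unblinding:

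- Assign each treatment-emergent event to the treatment state at onset or worsening, and judge worsening against the start of that state. Say also where onsets in the follow-up week are shown.
- Show separate columns for single-blind run-in placebo, double-blind placebo before V117957, V117957, double-blind placebo after V117957, and the washout week.
- Give person-time or exposure-adjusted rates in every column, because exposure is 6 weeks on V117957 and 1 to 2 weeks in each of the others.
- Keep the pooled double-blind placebo column beside the split columns. Placebo before V117957 should not be the only comparator: its double-blind data come from one sequence and the first two weeks only, about 44 person-weeks against 44 × 6 = 264 on V117957.

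The change is to analysis-plan and table-shell wording. It needs onset and dosing dates; the treatment-emergent definition already requires onset timing, and Table 1 has evening dosing recorded in the diary. The price is precision: each double-blind placebo column would hold about 22 subjects, so one subject moves its incidence by 1/22, or 4.5 points. The washout column also combines the first week after V117957 (Sequence A) with the third (Sequence B) and should be footnoted or shown by sequence.
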